**Table 4.1 Criteria of Early No-Go Decisions Based on DCR at 16 Weeks**

Number of Subjects with DCR at 16 weeks in Control Arm	Number of Subjects with DCR at 16 weeks in Experimental Arm
10	$\leq 7$
11	$\leq 8$
12	$\leq 8$
13	$\leq 9$
14	$\leq 10$
15	$\leq 11$
16	$\leq 12$
17	$\leq 13$
18	$\leq 14$
19	$\leq 15$
20	$\leq 16$
21	$\leq 17$
22	$\leq 19$
23	$\leq 20$
24	$\leq 21$
25	$\leq 23$
26	$\leq 24$
27	$\leq 26$
28	$\leq 28$
29	$\leq 29$
30	$\leq 30$

DCR = disease control rate.

Operating characteristics of this continuous monitoring method are presented in [Table 4.2](#) based on 10000 simulations using the prespecified TV.

**Table 4.2 Operating Characteristics of Continuous Monitoring for No-Go**

True $\delta$ (BM DCR = 60%)	All No-Go (Interim & final)	Early No-Go (Confirmed at final)
0%	68%	19% (18%)
5%	46%	11% (10%)
10%	25%	5% (4%)
15%	11%	2% (2%)
20%	3%	1% (0)
25%	1%	0 (0)

Criteria: Target Value (TV)  $\delta = 15\%$ ; No-Go:  $\Pr(\delta > TV) < 10\%$ ; Early No-Go:  $\Pr(\text{No-Go}) > 95\%$ ;  
BM DCR: Benchmark Disease Control Rate.

## 6 VERSION HISTORY

Version	Date	Summary of Changes	Reason for Change
1.0	01FEB2019	Initial document	Initial document
2.0	11DEC2019	

Revised the ITT definition

Clarifications added about including concurrently enrolled control subjects in efficacy analyses.

	

To be aligned with protocol AM3.

To address comments received from the format review meeting.

Administrative changes.

		
 
Modified/Added subgroups for efficacy analyses.
 
Added a missing superscript in the formula of PFS-12 testing.
 
Updated signature page to include new team members.
 
Post cCRT window adjusted to 42 days to match Protocol AM3.
 
Added language about coagulation and thyroid analyses.
 
	
3.0	14DEC2020	
 
Additional summaries added to Section 3.3.2.
 
New subgroups added to Section 3.4.4.
 
Added PFS-6 and PFS-9 in Section 3.4.5.
 
	
 
Layout update as per review comments from IA#1.
 

4.0	07FEB2023	
Updates made for final CSR delivery:
 
 
Section 3.3.1 updated to include listing of global/country situation disruptions.
 
Section 3.3.2 updated to describe categorization of platin.
 
Section 3.6.2 updated with minor clarifications as well as description of durvalumab imAE analyses.
 
Additional subgroup added to Section 3.4.4 for ORR.
 
Subgroup analyses included for PFS.
 
Section 3.4.2.4 (PFS) updated to include additional landmarks at 18 and 24 months.
 
Section 3.4.2.5 (OS) updated to include additional landmarks at 18 and 24 months.
 
Section 3.4.2.5 (OS) updated to include additional field for deriving last known alive date.
 
Section 3.4.4 updated to include forest plots for subgroup analyses of ORR and PFS.
 
Section 3.4.5 updated with clarification that unconfirmed ORR will also be reported.
 
iRECIST confirmed not to be reported in CSR (Section 3.4.5).
 
 
Other minor clarifications were made throughout.
	
 
Required listing to describe impact of COVID-19 on the study.
 
Previously this was not well-defined and had been subject to manual review. The team agrees all terms should be coded and therefore WHO Drug information can be used to derive categories.
 
Automatic adjudication of durvalumab imAEs is a required process. Outputs have been added to comply with this.
 
Disease stage at study entry (IIIA vs. IIIB/C) is considered a clinically important subgroup.
 
Though confirmed ORR is the primary endpoint, PFS is also clinically relevant and therefore subgroups will be explored.
 
Data maturity permits further landmarks to be presented.
 
Data maturity permits further landmarks to be presented.
 
Update provides further coverage of potential last known alive date and increased accuracy.
 
Forest plots provide a clear way to present subgroup results.
 
This is per the CSP but was not previously clarified in the SAP.
 
Confirmed with clinical team that iRECIST is not required for the CSR.
 

5.0	04SEP2023	
 
1. Added a few terms in the list of abbreviations
 
2. Section 3.1 clarified for the definition of baseline
 
3. Updated SAS version to 9.4
 
4. Table 3.2-1 Added PK-evaluable population
 
5. Section 3.3.3 removed data cut-off from duration of exposure definition
 
6. Section 3.3.4 add ATC and WHO Drug version
 
7. Section 3.3.5 Added COVID-19 related IPDs
 
8. Section 3.4.2.4 Added PFS-36 month landmark
 
9. Section 3.4.2.4 Updated and clarified the Greenwood's formula, and added more details
 
10. Section 3.4.2.5 Added OS-36 month landmark
 
11. Section 3.5 Updated section to clarify that no pharmacodynamic analyses are planned at this stage
 
12. Section 3.6 Added clarification regarding any derivation timeframe (in Labs, VS, ECOG)
 
13. Section 3.6.4 Updated wording to increase readiness and match what the expectations are, for the laboratory tables
 
14. Section 3.6.4 Creatinine clearance rate formula added
 
15. Section 3.6.5.1 Removed 10% subjects wording and added minimum and maximum post-baseline summaries of vital signs
 
16. Section 3.6.5.2 Added information as to why no ECG analyses are planned for the CSR
 
17. Section 3.6.5.4 Added a section for physical examinations (none planned)
 
18. Section 3.8 Added PK analysis plan
 
19. Section 3.8 Mentioned that all results to be reported in ug/mL
 
 
Other minor clarifications were made throughout.
	
 
1. Previously missing some abbreviations, and new ones corresponding to new updates
 
2. Lack of information in defining baseline when no time indicator captured
 
3. Latest SAS version available
 
4. SAP now includes PK analysis
 
5. No DCO defined in final CSR
 
6. Clarify that the summary of concomitant medications is by ATC and PT
 
7. COVID-19 related IPDs might be required for the CSR
 
8. Agreed with the team in prior communications to include PFS-18, PFS-24 and PFS-36 landmarks for the CSR
 
9. Lack of precision in the formula details (<math>n_i</math> refers to deaths or disease progressions in the PFS section, difference between <math>i</math> and <math>k</math>)
 
10. Agreed with the team in prior communications to include OS-18, OS-24, and OS-36 landmarks for the CSR
 
11. Previous version outdated (MedImmune process) - Wording confirmed with PK/PD team
 
12. Discussed during the Dry Run review with the team to consider only post-baseline visits up to and including 90 days post last dose of study drug
 
13. Wording was unclear and disorganized, clarification was needed
 
14. Information more complete with additional details provided
 
15. CSP doesn't mention a selection criterion (10% of subjects) so not needed here, but mentions min/max summaries of vital signs
 
16. CSP mentions ECG analyses while ECGs were only collected at screening
 
17. CSP mentions physical examination statistical analysis,
 

-----	-----------	--	--

			
but none are planned for the CSR (data do not allow)
 
18. After discussion with the study team and the PK/PD team, PK analysis plan needed to be included in the SAP. Previous version outdated (MedImmune process).
 
19. After discussing with the PK/PD team, Durvalumab serum concentrations should be converted from ng/mL to ug/mL

--	--	--	--

## 7 APPENDIX

### 7.1 Derivation of RECIST v1.1 Disease Assessment Overall Response

Guidance regarding the handling of dropouts and missing data will apply uniformly to all efficacy analyses resulting from an application of RECIST v1.1 to investigator assessed tumor measurements. For investigator reported outcomes, analyses will present outcomes reported by the investigator without consideration of missing data or censoring rules.

#### 7.1.1 Target Lesion Response

Target lesion response will be programmatically derived on the data collection instrument once RECIST v1.1 criteria are applied to the site personnel recorded target lesion measurements.

Possible values include:

- CR – Complete Response
- PR – Partial Response
- SD – Stable Disease
- PD – Progressive Disease
- NE – Non-evaluable
- NA – Not Applicable (*set value for all post-baseline disease assessments only if no target lesions are identified at baseline*)

The derivation for target lesion response is as follows (*please note the order of the algorithm below is important*):

1. If “Any Target Lesions Present” equals “No” on the *Target Lesions – Baseline* CRF, then all post-baseline “Target Lesion Response” equals “NA”.
2. Else, if “Percent Change from Nadir Sum of Diameters” is greater than or equal to 20% and the absolute increase from the nadir (defined as the “Total” for each post-baseline disease assessment minus the “Nadir Sum of Diameters”) is greater than or equal to 5 mm, then “Target Lesion Response” equals “PD”.
3. Else, if “Not Done” is selected, or “Measurement” is left blank, or “Lesion no longer Measurable” is selected and equal to “NE”, or “Lesion Intervention” is selected for any Target Lesion identified at Baseline, then “Target Lesion Response” equals “NE”.
4. Else, if “Total Non-Lymph Node” equals “0” and all Lymph Node Target Lesion “Measurements” are less than “10” individually, then “Target Lesion Response” equals “CR”.

Note: This step requires examining “Measurements” separately for Target Lesions with “Lymph Node” equal to “Yes” and “No”.

5. Else, if “Percent Change from Baseline Sum of Diameters” is less than or equal to -30%, then “Target Lesion Response” equals “PR”.
6. Else, “Target Lesion Response” equals “SD”.

If a subject has a missing tumor measurement at a disease assessment for 1 or more target lesions, the sum of diameters (longest for non-nodal lesions, short axis for nodal lesions) will be reported for the remaining target lesions. These data will be used to indicate radiologic disease progression if the sum of diameters for the observed lesions increases at least 20% from the nadir sum of diameters of all target lesions and demonstrates at least a 5 mm absolute increase from the nadir sum of diameters of all target lesions, in spite of the missing data (or if other criteria for PD are met).

### **7.1.2 Non-Target Lesion Response**

Non-target lesion response will be assigned by site personnel following a qualitative overall assessment of all non-target lesions.

Possible values include:

- CR – Complete Response

- Disappearance of all non-target lesions and normalization of tumor marker level. All lymph nodes must be non-pathological in size (<10mm short axis)
- Non-CR/Non-PD – Non-Complete Response / Non-Progressive Disease
  - Persistence of one or more non-target lesion(s) and/or maintenance of tumor marker level above the normal limits
- PD – Progressive Disease
  - Unequivocal progression of existing non-target lesions.
- NE – Non-evaluable
- NA – Not Applicable (*set value for all post-baseline disease assessments only if no non-target lesions are identified at baseline*)

Though non-target lesion responses are a subjective decision made by the site personnel, certain responses may be limited depending on the non-target lesion statuses recorded. An algorithm is provided below highlighting appropriate possible non-target lesion responses based on recorded data. Reaching a red box (■) signifies having reached the only allowable non-target lesion responses based on non-target lesion statuses. Reaching a green box (■) signifies having reached the end of the algorithm and more than one possible non-target lesion response is possible from which the Investigator may choose.

1. a) If no non-target lesions are identified at baseline, all post-baseline non-target lesion responses should equal NA. ■  
b) Else, if any non-target lesions are identified at baseline, responses may be limited to CR, Non-CR/Non-PD, PD, NE (i.e., responses of NA are not permitted).  
Go to Rule 2.
2. a) If all non-target lesions have a status are “Absent”, the responses may be limited to CR. ■  
b) Else, if at least one non-target lesion status is NOT “Absent”, the responses may be limited to Non-CR/Non-PD, PD, NE (i.e., responses of CR, NA are not permitted).  
Go to Rule 3.
3. a) If all non-target lesions have a status of “Unequivocal Progression”, responses may be limited to PD. ■  
b) Else, if no non-target lesions have a status of “Unequivocal Progression”, responses may be limited to Non-CR/Non-PD, NE (i.e., responses of CR, PD, NA are

not permitted).

Go to Rule 4.

c) Else, if at least one (but not all) non-target lesion has a status of “Unequivocal Progression”, the responses may be limited to Non-CR/Non-PD, PD, NE (i.e., responses of CR, NA are not permitted). (*Note: No response has been eliminated as an option here.*)

Go to Rule 5.

4. a) If all non-target lesions have a status of “Non-evaluable” and/or “Not Done” is selected, responses may be limited to NE. ■  
b) Else, if no non-target lesions have a status of “Non-evaluable” and “Not Done” is not selected, responses may be limited to Non-CR/Non-PD (i.e., responses of CR, PD, NE, NA are not permitted). ■  
c) Else, if at least one (but not all) non-target lesion has a status of “Non-evaluable” and/or “Not Done” is selected, the responses may be limited to Non-CR/Non-PD, NE (i.e., responses of CR, PD, NA are not permitted). ■  
(*Note: No response has been eliminated as an option here.*)
5. a) If all non-target lesions have a status of “Non-evaluable” and/or “Not Done” is selected, responses may be limited to NE. ■  
b) Else, if no non-target lesions have a status of “Non-evaluable” and “Not Done” is not selected, responses may be limited to Non-CR/Non-PD, PD (i.e., responses of CR, NE, NA are not permitted). ■  
c) Else, if at least one (but not all) non-target lesion has a status of “Non-evaluable” and/or “Not Done” is selected, the responses may be limited to Non-CR/Non-PD, PD, NE (i.e., responses of CR, NA are not permitted). ■  
(*Note: No response has been eliminated as an option here.*)

If a subject has a missing tumor status at a disease assessment for 1 or more non-target lesions, radiologic disease progression will be determined if the remaining non-target lesions qualitatively demonstrate unequivocal progression (or if other criteria for PD are met).

### 7.1.3 Disease Assessment Overall Response per RECIST v1.1

Investigator visit disease response will be programmatically derived on the data collection instrument using RECIST v1.1 criteria based upon target lesion response, non-target lesion response, and new lesion data. Missing values in any of target lesion response, non-target lesion response, and new lesion data will result in the disease response not being derived.

Possible values include:

- CR – Complete Response

- PR – Partial Response
- SD – Stable Disease
- PD – Progressive Disease
- NE – Non-evaluable

Target Lesion Response	Non-Target Lesion Response	New Lesion	Derived RECIST Disease Response
CR	CR or NA	No	CR
CR	Non-CR/Non-PD or NE	No (or NE)	PR
PR	CR or Non-CR/Non-PD or NE or NA	No (or NE)	PR
SD	CR or Non-CR/Non-PD or NE or NA	No (or NE)	SD
PD	Any	Any	PD
Any	PD	Any	PD
Any	Any	Yes	PD
NE	CR or Non-CR/Non-PD or NE or NA	No	NE
NA	CR	No	CR
NA	Non-CR/Non-PD	No	SD (Non-CR/Non-PD) a
NA	NE or NA	No (or NE)	NE
NA	CR or Non-CR/Non-PD	NE	SD (Non-CR/Non-PD) a

a Per RECIST v1.1, “SD (Non-CR/Non-PD)” is preferred over “SD” for non-target disease since SD is increasingly used as endpoint for assessment of efficacy in some trials so to assign this category when no lesions can be measured is not advised.

*(Note: “(or NE)” values under New Lesion will only be included in confirmation of progression or confirmation of new lesions are required per protocol. The last 4 rows may be eliminated from any study that requires identification of at least one measurable lesion at Baseline. One may choose to allow such cells to remain if an independent central review is included in the trial.)*

If a subject has a missing tumor measurement at some assessment(s) for 1 or more target lesions and criteria for PD are not otherwise met, an overall response of NE will be assigned for the assessment(s).

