#### **3.4.2.1 Best Overall Response**

Best overall response (BOR) will be based on all post-baseline disease assessments that occur prior to disease progression, and/or prior to the initiation of subsequent anticancer treatment. BOR will be summarized with the number and percentage of subjects for the following categories: complete response (CR); partial response (PR); stable disease (SD); progressive disease (PD); and non-evaluable (NE). At least 7 weeks (8 weeks minus 1 week to allow for the protocol-defined disease assessment window) from randomization of IP must elapse without a subsequently radiological disease progression to assign a best overall response of SD.

Confirmation of CR and PR is required and must occur at least 4 weeks after initial documentation of CR or PR. If CR is pending confirmation and is designated at an assessment followed by 1 or more NE assessments, and/or PR assessments such that 1) the Target Lesion Response is CR and the Non-Target Lesion Response is NE, or 2) the Target Lesion Response is PR due solely to an increase in one or more lymph nodes to a size  $\geq 10$  mm and the Non-Target Lesion Response is either CR or NE, CR may be confirmed thereafter. Similarly, if a PR is pending confirmation and is designated at an assessment followed by 1 or more NE and/or SD assessments, PR may be confirmed thereafter.

In general, subjects not classifiable under the RECIST v1.1 response categories due to insufficient data or early death will be classified as NE for BOR but will be counted in the denominator of all response rate calculations. This generalization includes if a subject has missing lesion data at baseline. In this scenario, the subject will be classified as NE for BOR.

If a subject is missing lesion data at a disease assessment and yet PD criteria is met despite the missing data, the subject will be classified as PD.

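### SAP 7.1.3 leaves a visit response underived when any component is blank, with no exception for PD, against seven other SAP provisions that keep PD; if applied, PFS and DoR events could be lost or dated late

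*SAP*

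**What the plan says.** SAP 7.1.3 combines target response, non-target response and new-lesion data into one visit response. It introduces the rule with "Investigator visit disease response will be programmatically derived on the data collection instrument using RECIST v1.1 criteria" and then adds "Missing values in any of target lesion response, non-target lesion response, and new lesion data will result in the disease response not being derived". No exception follows.

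Seven other provisions keep PD:

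- **7.1.3, table.** Three rows give PD when target is PD, when non-target is PD, or when there is a new lesion, with Any in the other columns.
- **7.1.3, closing sentence.** A missing target measurement leads to NE only where PD is not met in some other way.
- **3.4.2.1.** If lesion data are missing at an assessment but "PD criteria is met despite the missing data, the subject will be classified as PD".
- **7.1.1.** PD is checked before missing measurements are considered, and the closing text lets the observed lesions establish PD.
- **7.1.2, closing text.** With a non-target status missing, "radiologic disease progression will be determined if the remaining non-target lesions qualitatively demonstrate unequivocal progression".
- **7.1.5.** The PD date is the earliest of the target, non-target and new-lesion dates.
- **Table 3.4.1.** The PFS event is dated at the earliest sign of PD or death.

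Rule 5 of 7.1.2 has a related fault. It is reached only through rule 3c, when at least one but not all non-target lesions show Unequivocal Progression. Yet 5a limits the response to NE if all non-target lesions are Non-evaluable and/or Not Done is selected.

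**The concern.** A programmer who follows the 7.1.3 sentence and one who follows the table below it would derive different results from the same form. Take a scan with target PD and an empty new-lesion field: the sentence gives no response, the table gives PD.

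What is at stake is the event date for PFS, and through it DoR, since SAP 3.4.2.2 takes its PD, death or censoring date from PFS. If PD is not derived at its own visit, the subject is censored at the previous evaluable scan, has PD dated at a later scan, or has a later death counted instead. All three outcomes mean fewer or later events. The trial is open-label, the endpoints rest on investigator measurements, and the protocol (4.3.1) stores images only for possible central re-analysis. No planned second reading would therefore catch the loss.

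**Working it through.** The plan gives no figure for this point. The check is logical, followed by a bound on the effect of one lost event.

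**1. Combinations the sentence affects.** The inputs are the values allowed in SAP 7.1.1 to 7.1.3, plus blank:

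- target: CR, PR, SD, PD, NE, NA, blank (7)
- non-target: CR, Non-CR/Non-PD, PD, NE, NA, blank (6)
- new lesion: No, Yes, NE, blank (4)

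The counts, reading Any in the table as including blank, are:

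- All combinations: 7 × 6 × 4 = 168.
- No PD evidence: 6 × 5 × 3 = 90, so PD evidence: 168 − 90 = 78.
- PD evidence and nothing blank: (6 × 5 × 3) − (5 × 4 × 2) = 90 − 40 = 50.
- PD evidence and at least one blank: 78 − 50 = 28 (25 with one blank, 3 with two).

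Under the literal sentence all 28 are underived. Under the table's PD rows all 28 are PD.

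**2. Narrowing by the plan's own coding.** Step 3 of 7.1.1 codes a blank target measurement as NE, after the PD check. If the target component is therefore never blank: (6 × 6 × 4) − (5 × 5 × 3) − 50 = 144 − 75 − 50 = 19 remain. If a non-target assessment marked Not Done is also coded NE: (6 × 5 × 4) − (5 × 4 × 3) − 50 = 120 − 60 − 50 = 10 remain. All 10 have a blank new-lesion field, five with target PD and five with non-target PD only. These are logical combinations, not patients.

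**3. Effect of one lost event on PFS-12.** Inputs: 60 subjects per arm (SAP 2.4). Assumptions for illustration, not in the documents: 27 PFS events by month 12 and no other censoring before then.

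- All events kept: 33/60 = 55.0%.
- Earliest event lost, subject censored before any other event: 33/59 = 55.9%, a gain of 0.9 points.
- Latest event lost, subject censored after the other 26 events: 34/60 = 56.7%, a gain of 1.7 points.

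The ceiling of 1/60 = 1.7 points does not depend on the 27, but it does depend on no other censoring. With earlier censoring, each Kaplan-Meier step is larger than 1/60.

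**4. Response endpoints.** BOR uses only assessments before progression (SAP 3.4.2.1), so SD or a confirmed response reached before PD stands whether or not the PD is derived. PD at the first scan would become NE, and neither counts as response or disease control. An underived week-16 scan does not supply the SD of at least 16 weeks required by 3.4.2.3. Only an unusual later non-PD scan could change BOR.

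**5. Rule 5a.** Once one lesion shows Unequivocal Progression, the lesions cannot all be Non-evaluable, so that half of 5a cannot occur. If Not Done is a separate trigger, 5a forces NE despite recorded progression, while 5c would allow PD on the same trigger. If Not Done is read per lesion, 5a can never be reached. Neither reading gives 5a a valid use.

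**The case against.** The strongest reply is scope. The sentence concerns the investigator visit response on the data collection instrument, the endpoints apply RECIST to investigator measurements (SAP 3.4.2), and 7.1.5 allows the two to differ. This has weight but does not settle the matter. Section 3.4.2 names Appendix 7.1 as the derivation guidance, 7.1.1 uses the same instrument wording for target response, and nothing says which rule prevails.

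A second reply is that missing lesions within a component, covered in 7.1.1 and 7.1.2, are not the same as a missing component, and that Any in the table may mean any listed value. That is fair. It leaves 3.4.2.1, 7.1.5 and Table 3.4.1, which keep PD without such a limit.

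A reader might infer that the plan removes documented progression from BOR, DCR, DoR and PFS. The documents do not support that. It would require one sentence to override seven provisions, and step 4 above shows that BOR and DCR barely move. Nor is an underived PD usually unrecoverable. Without clinical deterioration, protocol 4.3.1 requires a confirmatory scan, and a confirmed PD takes the initial scan's date. PD may therefore be dated late rather than lost. Loss is more likely when no confirmatory scan is due, since the end-of-study visit (protocol Table 7) lists no scan among its visible procedures.

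Data queries and source verification (protocol 6.4 and 6.2) should also keep blank fields few. On rule 5, the algorithm only says responses may be limited, and the closing text of 7.1.2 keeps PD. This softens the fault without removing the contradiction.

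**Conclusion.** The concern holds as an internal contradiction with a conditional consequence. Confidence is high that the 7.1.3 sentence conflicts with the rest of the SAP, and moderate that it would affect results.

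If the sentence governs the analysis, PFS and DoR shift towards fewer or later events in any arm with blank components beside PD. ORR, the primary endpoint, is essentially untouched, as are BOR and DCR. The total effect cannot be stated, because the documents give no rate of blank fields. The per-event bound of about 1.7 points of PFS-12 assumes 60 subjects and no other censoring before month 12. Any distortion of the comparison between arms further depends on how unevenly blanks fall, which is also not given.

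**What to change.** 1. In SAP 7.1.3, add to the missing-value sentence: *unless another component shows PD, in which case the response is PD*.
2. Leave the handling of non-PD visits unchanged. A general rule coding blank components as NE should not be adopted: the table gives PR for target PR with non-target NE and new lesion No (or NE), so incomplete forms could create responders on the primary endpoint.
3. State whether the instrument field or the analysis derivation governs the endpoints.
4. In 7.1.2, delete rule 5a. Rules 5b and 5c cover every case that can reach rule 5, and both keep PD available.

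The cost is a few lines of SAP text and a small programming change, with a check of visits that have a blank component beside PD. No sample size or operating characteristic changes.
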